7.4 Study procedures narrative

Due to the innate differences in the pathology, natural history and differences in current standard of care for primary and metastatic brain tumors this pilot study will have two arms:

ARM 1: Metastatic brain tumors - Melanoma

ARM 2: Primary brain tumor - Glioblastoma multiforme (GBM)

All subjects will receive standard of care treatment for their respective arms as described in section 7.6.

All subjects will receive pembrolizumab (200 mg IV every 3 weeks) starting on the first day of radiation until persistent radiographic progression is confirmed, in addition to standard of care for their respective arms. Clinical MRI scans will be performed to assess response to therapy. Clinical standard of care MRIs are done at baseline, 4 weeks after the last day of radiation and then every 9 weeks thereafter until suspected radiographic progression. Early follow up clinical standard of care MRI (and ferumoxytol steady state MRI, see below) will be performed 4 weeks from the date of MRI showing suspected radiographic progression to confirm persistent radiographic progression (all timepoints \pm 5 days). Patients with imaging evidence of suspected radiographic progression may continue with one additional cycle of pembrolizumab. The decision regarding continuation of pembrolizumab will be made by the principle investigator based on clinical findings that include (1) stable ECOG performance status with no more than 8mg of dexamethasone (or equivalent) a day; (2) absence of new or worsening symptoms not managed with steroids; and (3) absence of progressive tumor at critical anatomical sites (e.g., spinal cord compression) requiring urgent alternative medical intervention.

Additional ferumoxytol steady state MRIs will be done at baseline, 4 weeks after the last day of radiation, at suspected radiographic progression and within 4 weeks from suspected radiographic progression to confirm persistent radiographic progression (all timepoints \pm 5 days). During this follow up period, subjects will be followed with a clinical exam weekly to monitor for clinical stability.

When persistent radiographic progression is confirmed, subjects will be evaluated for a craniotomy with intent to complete resection and/or biopsy of the enhancing lesion, if this is thought to be the clinical standard of care.

When there is radiologic progression after radiation, current standard of care includes repeat craniotomy to confirm true vs pseudoprogression. Biopsy tissue obtained from surgery at persistent radiographic progression will be evaluated by the pathologists at OHSU. The pathologist will determine if the tissue is consistent with progression or pseudoprogression, where progression is defined as presence of viable metastatic carcinoma in the biopsy tissue and absence of tumor cell is assumed to reflect pseudoprogression. If histopathology confirms pseudoprogression the subject will continue on pembrolizumab every 3 weeks until further radiographic progression is suspected. If histopathology confirms progression, the subject will be removed from the study, followed clinically with serial clinical standard of care MRIs every 3 months for up to a year and then every 6 months until death or lost to follow-up.

Standard of care surgery or biopsy is performed only if 1) the lesion is deemed easily accessible 2) surgery is not expected to worsen neurological outcomes and 3) it is in the best clinical interest of the patient. The decision regarding surgery will be consensus based and when possible, will be made after each individual case has been presented at the OHSU multidisciplinary brain tumor board. If a subject is not a surgical candidate, or is unwilling to undergo surgery, they will be taken off study. They will, however, be eligible for continuation of pembrolizumab, at the physician's discretion, at the same dose and frequency, if clinical benefit is noted. They will be followed clinically with serial clinical standard of care MRI scans as described in section 7.11.

In subjects where the lesion remains unchanged or regresses in volume at 4 weeks (± 5 days) after the date of suspected radiographic progression, pembrolizumab will be continued until further persistent radiographic progression is confirmed.

All subjects will be followed with clinical examination and clinical standard of care MRI scans until death or lost to follow up. Subjects will be treated for up to 2 years, toxicity, or progression whichever comes first. Dose reductions/discontinuations for pembrolizumab will be as per Merck guidelines.

Subjects can restart pembrolizumab within 2 weeks after surgery. If the subject has a surgical complication that will prevent them from starting pembrolizumab within 2 weeks, the PI will discuss these cases with Merck & Co on a case by case basis. However, if pathology suggests pseudoprogression, pembrolizumab will be restarted 30 days (± 5 days) after surgery.

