progression or toxicity. Ferumoxytol MRI (FeMRI) will be performed in the same day and sitting as the clinical MRI at baseline and 4 weeks after the last day of radiation timepoints. FeMRI may be performed independently (on a different day or different MRI setting) of the clinical MRI if there is suspected radiographic progression or to confirm radiographic progression. If there is suspected progression, subjects undergo a ferumoxytol steady state MRI and continue on pembrolizumab for one more cycle. The decision regarding continuation of pembrolizumab will be made by the principle investigator based on clinical findings that include (1) stable ECOG performance status with no more than 8mg of dexamethasone (or equivalent) a day; (2) absence of new or worsening symptoms not managed with steroids; and (3) absence of progressive tumor at critical anatomical sites (e.g., spinal cord compression) requiring urgent alternative medical intervention. Follow up clinical standard of care and ferumoxytol MRIs will be repeated to confirm persistent radiographic progression in 4 weeks. During this 4 week follow up period, subjects will be followed with a clinical exam weekly to monitor for clinical stability. If the 4 week follow up scan confirms progression (as defined in section 8.1), then pembrolizumab is discontinued and subject is evaluated for clinical indication of standard of care surgery or biopsy. Surgery or biopsy is performed only if 1) the lesion is deemed easily accessible 2) surgery is not expected to worsen neurological outcomes and 3) it is in the best clinical interest of the subject. The decision regarding surgery will be consensus based and when possible, will be made after each individual case has been presented at the OHSU multi-disciplinary brain tumor board. If histopathology confirms pseudoprogression or is inconclusive, the subject will continue on pembrolizumab every 3 weeks until further radiographic progression is suspected. If histopathology confirms progression, the subject will be removed from the study. Subjects with evidence of new lesions distant from the primary lesion/s (not present at entry to the study) in the CNS or systemically that fulfil criteria for progression by immune related response criteria (irRC)[1] will be taken off study drug, but will be followed with serial clinical standard of care MRI.

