- **Confirmation of true progression:** For the purpose of this study, Histopathologic evidence of viable tumor cells in patients with persistent radiographic progression will be define to have confirmed true progression. True progression is confirmed by histopathology, Pembrolizumab will be stopped and patient swill be taken off-study.. Patients who refuse biopsy or biopsy is not deemed clinically necessary will be taken off study at persistent radiographic progression. However, they will be continued to be monitored with clinical MRI scan and until death.
- **Pseudoprogression (PsP):** for the purpose of this pilot study, PsP may be confirmed by imaging or by pathology.
 - PsP Imaging: stable or decrease in volume of enhancement at 4 weeks (\pm 5 days) after suspected radiographic progression.
 - PsP pathology: No viable tumor tissue is seen by histopathology evaluation on tissue obtained after confirmed radiographic progression by imaging.
- **Clinical progression:** Subjects may be removed from study if they experience symptomatic deterioration without radiographic evidence of disease progression.

Not evaluable (NE): Only relevant if any of the target lesions had additional interventions for clinical managements, patient is unable to get follow up scans or images are of poor quality.

Duration of Best Response: The duration of best response is measured from the time measurement criteria are met for SD, CR or PR (whichever is first recorded) until the first date that recurrent or PD is objectively documented (taking as reference for PD the smallest measurements recorded since the treatment started).

Progression free survival and overall survival will be calculated from the date of diagnosis to the date of confirmed progression or death, respectively. The date of diagnosis was used because the time between the date of diagnosis and the start of treatment or date of enrollment may vary due to subject variables or logistical issues based on radiation planning.

Systemic Lesions (only for Arm 1):

Measurements based on RECIST version 1.1 will be used to make a diagnosis of suspected systemic progression; it will be confirmed using irRC at follow-up.

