8.2 Image processing

Image processing will be done at OHSU.

8.2.1 For CNS lesions:

SS-CBV maps will be created using the high resolution T2*w scans before and after contrast agent and $\Delta R2^*$ maps will be created using the formula $\Delta R2^* = \ln(SI_{pre}/SI_{post})/TE$, in which SI_{pre} and SI_{post} indicate the signal intensities pre- and post ferumoxytol, and TE is the echo time. DSC-CBV maps from gadoteridol DSC will be created using a mathematical leakage correction method in NordicICE (Nordic Neurolab, Bergen, Norway) an FDA approved perfusion MRI software (if gadoteridol could not be given per institutional protocol (see protocol below) ferumoxytol enhancement will be used). The coregistration and overlay of CBV maps on T1-w MPRAGE will be done using NordicICE as well [27, 33]. The clinical MR sequences, such as T1 weighted scans with and without gadoteridol, and T2 weighted pre contrast scans will also be read. Images will be read by 2 radiologists. The radiologists will be blinded to the type of CBV maps (SS and DSC) and subject information.

8.2.2 Oregon Health & Science University policy on assessment of lab results prior to gadolinium based contrast media

For patients with the following risk factors, a serum creatinine level will be obtained with calculation of eGFR according to the following guidelines:

- 1) Creatinine/eGFR NOT required:
 - Dialysis patients – No eGFR required
 - Dialysis patients are excluded from the requirements in numbers 2 and 3 below.
- 2) Creatinine/eGFR required within 24 hours of MRI scan:
 - All inpatients (includes Daypatients and ER patients)
 - Outpatients whose most recent eGFR<60
- 3) Creatinine/eGFR required within 30 days of MRI scan:

- Patients >60 years of age
- Outpatients with a history of hypertension requiring medication
- Outpatients with diabetes mellitus
- Outpatients with kidney disease: kidney transplant, single kidney, kidney cancer, kidney surgery
- Outpatient children < 1 year of age

The technologist or RN will notify the radiologist for the following:

- 1) Patient has a history of NSF (Nephrogenic Systemic Fibrosis)
- 2) Patient is on dialysis
- 3) Patients with eGFR <30 mL/min/1.73m²
- 4) Patient received gadolinium based contrast media within the past 24 hours
- 5) For questions related to kidney function or patient history

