10.0 STATISTICAL ANALYSIS PLAN

Given the exploratory nature of this study, the statistical analyses will be descriptive in nature. For the primary and secondary objectives, sensitivity, specificity, rate of adverse event and distribution of best responses will be analyzed using proportions and exact 95% confidence intervals. Progression free survival and overall survival will be assessed using the Kaplan-Meier product limit estimates. Outcomes in the exploratory objectives will be summarized using descriptive statistics as appropriate; and associations between immunological parameters, PDL-1 expression, clinical responses, radiological responses and other variables will be explored using two sample tests or correlation measures, as appropriate.

Power and sample size calculation for Arm 1

The accrual to arm 1 is stopped with 2 patients. These 2 patients will be described separately and no further analysis will be done.

Power and sample size calculation for Arm 2

For arm 2, we will enroll 43 GBM patients. Here we roughly estimate the precision of sensitivity and specificity in the primary objective based on these 43 patients.

In subjects with GBM, we anticipate to have only one lesion/subject. We assume that all subjects will eventually have disease progression and due to dropout and inoperable cases, a total of $n = 32$ subjects will undergo surgery to provide histopathological data on disease progression. Further, we assume that 40% of the $n = 43$ subjects will develop pseudo-progression and be observed based on follow-up scan.

For sensitivity, further assume that out of the $n = 32$ subjects who will undergo surgery, 26 subjects will have true progression based on pathology (gold standard). Then based on $n = 26$,

if we observe 22 subjects (lesions) for whom the true progression is correctly identified by Ferumoxytol MRI, then the sensitivity will be 85% with a 95% CI between 65% and 96% (Table XX).

Number of subjects (lesions) with true progression	Number of subjects (lesions) whose true progression was detected by Ferumoxytol MRI	Sensitivity	Exact 95% CI of Sensitivity
26	26	100%	87% to 100%
26	24	92%	75% to 99.1%
26	22	85%	65% to 96%
26	20	77%	56% to 91%
26	18	69%	48% to 86%
26	16	62%	41% to 80%

Table 12: Estimated sensitivity and 95% CI based on 26 subjects (lesions).

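### The protocol does not require the pathologists who set the reference standard to be masked to ferumoxytol rCBV, so sensitivity and the surgical part of specificity may be biased upward

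*Combined protocol and SAP*

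**What the plan says.** **Who sets the label.** Section 7.4: "Biopsy tissue obtained from surgery at persistent radiographic progression will be evaluated by the pathologists at OHSU", followed by "The pathologist will determine if the tissue is consistent with progression or pseudoprogression". Section 10 builds the sensitivity calculation on this label, assuming that "26 subjects will have true progression based on pathology (gold standard"). It restricts primary sensitivity to patients with surgical results. Specificity uses pseudoprogression established by surgery or by follow-up scan.

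**The criterion.** Section 8.1 defines true progression by "Histopathologic evidence of viable tumor cells in patients with persistent radiographic progression" and pathological pseudoprogression by "No viable tumor tissue is seen by histopathology evaluation on tissue obtained after confirmed radiographic progression by imaging". Section 7.4 words the progression side in terms of metastatic carcinoma, which does not fit glioblastoma, the only tumour still enrolling.

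**A third outcome.** Section 2.0: "If histopathology confirms pseudoprogression or is inconclusive, the subject will continue on pembrolizumab every 3 weeks until further radiographic progression is suspected". Sections 6.0 and 7.6 repeat this. Sections 7.4 and 8.1 omit it, and section 10 does not say how such a case is counted.

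**Order of events.** Sections 2.0, 6.0 and 7.4 place a ferumoxytol MRI at suspected progression and another about 4 weeks later, both before surgery. The decision to operate, when possible, "will be made after each individual case has been presented at the OHSU multi-disciplinary brain tumor board".

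**Masking.** Sections 7.6 and 8.2.1 cover the image readers: "The radiologists will be blinded to the type of CBV maps (SS and DSC) and subject information". Section 7.14 calls the trial open label and 7.20 marks blinding as not applicable. I found no sentence on what imaging information the pathologist may or may not see (a few front-matter and section 4 pages were not in the text I read).

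**The concern.** The primary objective is the accuracy of rCBV against tissue. If the person calling the tissue knows the rCBV result, a doubtful specimen may be called to agree with it. This is review bias in the reference standard. A swayed call moves toward agreement, so it tends to raise both accuracy measures, and masking the image readers does nothing to prevent it.

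The setting makes the gap worth closing. Tissue and imaging are handled at one centre. Section 3.4 states the expectation that rCBV will separate the two conditions accurately, and section 4.3.1 says the study will validate the method. Section 3.2 says the pilot data will be used to power a larger study, so an optimistic estimate would be carried forward. With 26 planned progression cases, one or two calls visibly move the estimate.

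**Working it through.** **Inputs from section 10.** 43 patients, 32 operated, 26 with true progression on pathology; example sensitivity 22/26; 17 with pseudoprogression; example specificity 15/17; rCBV cutoff 1.75.

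**Reproducing the plan.** Exact (Clopper-Pearson) limits for x of n are the 0.025 quantile of Beta(x, n − x + 1) and the 0.975 quantile of Beta(x + 1, n − x).
- 22/26 = 84.6%, 95% CI 65.1% to 95.6% (plan: 85%, 65% to 96%)
- 15/17 = 88.2%, 95% CI 63.6% to 98.5% (plan: 88%, 64% to 99%)

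All rows of Tables 12 and 13 reproduce to rounding.

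**Illustration 1: individual calls change.** The numbers of re-called cases are assumptions; the documents give none.

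If f missed cases (progression on tissue, rCBV below 1.75) are re-called as pseudoprogression, each leaves the sensitivity denominator and becomes a correct negative:
- Sensitivity = 22/(26 − f)
- Specificity = (15 + f)/(17 + f)

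If g operated false positives are re-called as progression:
- Sensitivity = (22 + g)/(26 + g)
- Specificity = 15/(17 − g)

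| Re-called | Sensitivity (95% CI) | Specificity (95% CI) |
|---|---|---|
| none | 22/26 = 84.6% (65.1–95.6) | 15/17 = 88.2% (63.6–98.5) |
| f = 1 | 22/25 = 88.0% (68.8–97.5) | 16/18 = 88.9% (65.3–98.6) |
| f = 2 | 22/24 = 91.7% (73.0–99.0) | 17/19 = 89.5% (66.9–98.7) |
| g = 1 | 23/27 = 85.2% (66.3–95.8) | 15/16 = 93.8% (69.8–99.8) |

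Missed cases mainly move sensitivity; false positives mainly move specificity. Both routes push both measures upward.

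**Illustration 2: a fraction e of all operated specimens is equivocal and always follows rCBV.** Assume that the 32 − 26 = 6 operated patients without true progression are among the 17 with pseudoprogression and share their false-positive rate. Operated false positives are then 6 × 2/17 = 0.706.
- Sensitivity(e) = (22 + 0.706e) / (22 + 0.706e + 4(1 − e))
- Specificity(e) = (15 + 4e) / (15 + 4e + 2 − 0.706e)

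| e | Sensitivity | Rise from 84.6% | Specificity |
|---|---|---|---|
| 5% | 22.035/25.835 = 85.3% | 0.7 | 15.2/17.165 = 88.6% |
| 10% | 22.071/25.671 = 86.0% | 1.4 | 15.4/17.329 = 88.9% |
| 20% | 22.141/25.341 = 87.4% | 2.8 | 15.8/17.659 = 89.5% |
| 30% | 22.212/25.012 = 88.8% | 4.2 | 16.2/17.988 = 90.1% |

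The range for e is assumed, and so is perfect adherence to rCBV; partial influence would give smaller shifts.

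**The case against.** A reader might infer that the pathologists are unmasked and that sensitivity is therefore inflated. The documents do not support this.
- They are silent on what the pathologist sees. The open-label statement in 7.14 concerns the treatment given, not imaging results.
- The tumour board decides about surgery. Nothing says that rCBV is shown there or that the reporting pathologist attends.
- The scans precede the tissue, but 7.6 and 8.2.1 give no time for the two-radiologist read. The route to surgery in 8.1 runs on enhancement volume, not rCBV.

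A reader might also infer that mixed tissue forces an arbitrary choice between two labels. That too goes beyond the text. Under 8.1, viable tumour makes the specimen progression however much treatment effect surrounds it, and 2.0, 6.0 and 7.6 allow an inconclusive result. Judgement remains over whether cells are viable tumour, but the room for influence is narrower than a free choice. A doubtful specimen left as inconclusive need not move toward rCBV at all.

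Finally, the analysis is descriptive with no hypothesis test, and a shift of 0.7 to 4.2 points is small beside an interval about 30 points wide.

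These points limit the claim to a possible bias of unknown size. They do not remove it. The interval describes sampling error, whereas bias moves the whole interval: two re-called cases lift the lower limit from 65.1% to 73.0%. Nothing in the plan rules this out.

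**Conclusion.** The point stands as a gap in how the reference standard is obtained. Masking of the pathologists to the index test is not required, the scans come first, the call involves judgement, and section 10 has no place for inconclusive tissue. Upward bias is possible in sensitivity and in the surgically confirmed part of specificity. Pseudoprogression labelled by follow-up scan is not exposed by this route.

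The size cannot be established from the documents. The figures above rest on assumed numbers of re-called cases or on an assumed equivocal fraction of 5% to 30% that always follows rCBV. They show how sensitive the estimates are to a few calls; they do not estimate an actual bias. The change is worth making because it is cheap and protects the primary endpoint.

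**What to change.** **Sections 7.4 and 8.1.** State that the study label (viable tumour present, absent, or inconclusive) is recorded on a study form by an existing OHSU pathologist without access to the ferumoxytol report or rCBV. Leave rCBV off the pathology request. Lock the label before any post-surgical discussion of imaging. The tumour board meets before tissue exists, so a lock cannot protect against what was said there; where possible, use a pathologist who did not see rCBV at that meeting. Routine clinical reporting is unchanged.

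**Section 10.** State that inconclusive specimens are left out of primary sensitivity and specificity, and counted each way in a supporting analysis.

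**Specimens already reported.** Report, as a limitation, whether rCBV was available to the pathologist. A re-read of existing slides is optional: the same pathologist may recall the case, and section 12.4 has study samples destroyed after analysis, so slide availability would need checking.

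**Cost.** A short form and minor logistics. No extra reader or tissue is needed for the prospective change, and the planned numbers and Tables 12 and 13 stay as they are.

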5.2 Subject Inclusion Criteria

In order to be eligible for participation in this trial, the subject must:

1. Be willing and able to provide written informed consent/assent for the trial.
2. Be ≥ 18 years of age on day of signing informed consent.
3. Have a life expectancy of at least 6 months.
4. Have a histologically confirmed diagnosis of: newly diagnosed glioblastoma (WHO Grade IV)
5. Have ECOG performance status of 0 or 1 on stable or reducing dose of steroids for symptom management (not more than 8 mg of dexamethasone or equivalent per day) for 5 days prior to enrollment. Change in glucocorticoid dose for any purpose other than to modulate symptoms from an adverse event. *Note: The use of physiologic doses (e.g., prednisone 10 mg) of corticosteroids may be approved after consultation with Merck & Co. Use of prophylactic corticosteroids to avoid allergic reactions (e.g. IV contrast dye) is permitted.*
6. At least 14 days from any major surgeries including brain biopsy before the start of study drug pembrolizumab.
7. Demonstrate adequate organ function as defined in Table 3.
8. Female subject of childbearing potential should have a negative urine or serum pregnancy within 72 hours prior to receiving the first dose of study medication. If the urine test is positive or cannot be performed or confirmed as negative, a serum pregnancy test will be required.
9. Female subjects of childbearing potential should be willing to use 2 methods of birth control or be surgically sterile, or abstain from heterosexual activity for the course of the study through 120 days after the last dose of study medication. Subjects of childbearing potential are those who have not been surgically sterilized or have not been free from menses for > 1 year. Male subjects should agree to use an adequate method of contraception, including but not limited to, abstinence from heterosexual activity starting with the first dose of study therapy through 120 days after the last dose of study therapy.
10. Subject is eligible for and agrees to receive standard of care radiation and temozolamide after biopsy or maximum safe surgical resection.

Table 3 Adequate Organ Function Laboratory Values

System	Laboratory Value
--------	------------------

Hematological	
Absolute neutrophil count (ANC)	≥1,500 /mcL
Platelets	≥100,000 / mcL
Hemoglobin	≥9 g/dL or ≥5.6 mmol/L without transfusion or EPO dependency (within 7 days of assessment)
Renal	

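### Section 7.4 gives a histologic definition of progression that glioblastoma cannot meet and that conflicts with 8.1; Section 10 does not say which applies or how inconclusive tissue is analysed

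*Combined protocol and SAP*

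**What the plan says.** Section 7.4, which opens by covering both arms, has the pathologist decide between progression and pseudoprogression, "where progression is defined as presence of viable metastatic carcinoma in the biopsy tissue and absence of tumor cell is assumed to reflect pseudoprogression". Section 5.2 now admits only "newly diagnosed glioblastoma (WHO Grade IV"). Section 10 reports that Arm 1 stopped with 2 patients and will get no further analysis.

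Section 8.1, headed as the definitions for response assessment, words it differently: "Histopathologic evidence of viable tumor cells in patients with persistent radiographic progression will be define to have confirmed true progression". Its pathology route to pseudoprogression is "No viable tumor tissue is seen by histopathology evaluation on tissue obtained after confirmed radiographic progression by imaging". It also has an imaging route, "PsP Imaging: stable or decrease in volume of enhancement at 4 weeks" after the suspicion.

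Section 2.0 recognises a third histology result: "If histopathology confirms pseudoprogression or is inconclusive, the subject will continue on pembrolizumab every 3 weeks until further radiographic progression is suspected". Sections 6.0 and 7.6 (imaging schedule, Arm 2) repeat it. Sections 7.4, 8.1 and 10 do not mention it.

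Section 10 takes pathology as the gold standard for sensitivity. For specificity it uses surgical results or the follow-up scan. It refers to neither 7.4 nor 8.1.

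**The concern.** Histology is the sole reference standard for the primary sensitivity and part of the reference standard for the primary specificity. The protocol states it in two incompatible ways, and the one addressed to the pathologist describes a tumour that no subject in the analysed arm has. The wording appears to be left over from a metastatic cohort; Sections 3.4 and 8.3.2 still speak of lung biopsies, and Section 4.0 of NSCLC brain metastases.

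A second weakness does not depend on that wording. Under both 7.4 and 8.1, tissue in which no tumour is seen is pseudoprogression. Neither section asks whether the sample represented the lesion, although Sections 2.0 and 7.4 allow biopsy as well as resection. A true progression that was missed by sampling would leave the sensitivity denominator and enter the specificity denominator, where a high rCBV counts as a false positive. Because inconclusive histology has no analysis rule, its place in either denominator would be settled after the data are seen.

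**Working it through.** **Inputs, all from Section 10.** 43 glioblastoma subjects; 32 operated; 26 with true progression on pathology; 17 with pseudoprogression (40% of 43 = 17.2); rCBV cutoff 1.75; exact 95% intervals. Illustrative results: 22 of 26 and 15 of 17 correctly identified.

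**Step 1: the plan's figures.** The exact (Clopper-Pearson) limits for x of n are the 2.5% quantile of Beta(x, n − x + 1) and the 97.5% quantile of Beta(x + 1, n − x).

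- Sensitivity 22/26 = 84.6% (65.1 to 95.6); the plan has 85% (65 to 96).
- Specificity 15/17 = 88.2% (63.6 to 98.5); the plan has 88% (64 to 99).

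All ten rows of Tables 12 and 13 reproduce after rounding.

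**Step 2: the two rules side by side, for the 32 operated subjects.**

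| Specimen | Expected number | Under 7.4 | Under 8.1 |
|---|---|---|---|
| Viable glioblastoma cells | 26 | neither category | true progression |
| No tumour seen | at most 32 − 26 = 6 | pseudoprogression | pseudoprogression |
| Inconclusive | not given | not addressed | not addressed |

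Under a literal 7.4 the sensitivity denominator is 0 and sensitivity cannot be estimated. Under 8.1 it is 26 and nothing in Table 12 or 13 changes. Section 10 does not say whether the other 6 operated subjects are pseudoprogression or inconclusive.

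**Step 3: the tumour-free rule.** The documents give no sampling-failure rate, so this step is an assumption shown over a range. Let m of the 26 true progressions yield tumour-free tissue, and let h of those have rCBV at or above 1.75, with h = m × 22/26 rounded to a whole subject. Then

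- specificity = (15 + m − h)/(17 + m)
- sensitivity = (22 − h)/(26 − m)

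| m | h | Specificity (exact 95% CI) | Sensitivity |
|---|---|---|---|
| 0 | 0 | 15/17 = 88% (64 to 99) | 22/26 = 85% |
| 1 | 1 | 15/18 = 83% (59 to 96) | 21/25 = 84% |
| 3 | 3 | 15/20 = 75% (51 to 91) | 19/23 = 83% |
| 6 | 5 | 16/23 = 70% (47 to 87) | 17/20 = 85% |

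Sensitivity barely moves but loses subjects. Specificity carries the bias.

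**Step 4: one added specimen.** The denominator grows with each addition. A high-rCBV specimen takes 15/17 to 15/18, a change of 83.3 − 88.2 = −4.9 points. A low-rCBV specimen takes it to 16/18 = 88.9%, a change of +0.7.

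**The case against.** The best reply is that Section 8.1 is the definitions section, speaks for the study as a whole, does not depend on tumour type and is workable for glioblastoma. A pathologist looking at viable glioblastoma would very probably report progression whatever 7.4 says. The study is a descriptive pilot with no formal hypothesis, and aligning 7.4 with 8.1 changes no planned number. All of that stands. It does not settle which text governs, because no section gives 8.1 precedence and Section 10 cites neither.

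A reader might infer more than the documents support:

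- *That the gold standard is simply wrong for the open arm.* It is contradictory and unspecified; one of the two definitions is usable.
- *That under 7.4 all 32 operated subjects become pseudoprogression.* That category requires tumour cells to be absent, so the 26 with glioblastoma cells would be unclassified and at most 6 would be pseudoprogression.
- *That each doubtful specimen costs specificity a fixed 1/23 to 1/17, about 4 to 6 points.* Step 4 shows that the change depends on the rCBV of the specimen and can be slightly upward.
- *That inconclusive specimens are counted as pseudoprogression.* Section 2.0 lists the two as separate results with a shared treatment consequence. For the analysis, the plan is silent.

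Resection is also a possible tissue source, so small biopsies should not be presumed to dominate.

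**Conclusion.** The point holds as a contradiction in the reference standard for the primary objective, together with a missing analysis category. The literal effect of 7.4 is a sensitivity denominator of 0 instead of 26; the effect of following 8.1 is none. Correcting the wording is therefore necessary but does little by itself.

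The more substantive part is the unconditional reading of tumour-free tissue as pseudoprogression, which 8.1 shares, and the absence of any rule for inconclusive tissue. Its possible size is a fall in specificity from 88% to 83% for one missed progression, 75% for three and 70% for six. Those figures rest on the plan's illustrative counts, an assumed number of sampling failures and the assumption that most such lesions have high rCBV. They show sensitivity to the rule and do not predict what will be observed.

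**What to change.** 1. Replace the 7.4 wording so that its classification of tissue matches 8.1, and cite that single definition in Section 10 as the reference standard for the analysis.
2. In Section 10, add a category for inconclusive or non-representative tissue, stating in advance what places a specimen in it. Exclude it from both primary denominators and report the number excluded.
3. Add two bounding sensitivity analyses. With k excluded specimens, h of them at or above the cutoff, and primary results a/n for sensitivity and b/p for specificity: counting all as true progression gives sensitivity (a + h)/(n + k); counting all as pseudoprogression gives specificity (b + k − h)/(p + k).

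The cost is a short text amendment to 7.4 and Section 10, with no added tissue, imaging or staff. The downside is possibly a few subjects fewer in the primary set and so slightly wider intervals.

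The same histology result also governs continuing pembrolizumab and removal from study. Sections 2.0, 6.0 and 7.6 give a consequence for inconclusive tissue that 7.4 and 8.1 lack, so the sponsor must reconcile these sections. This point concerns classification for the analysis and does not say which clinical rule is right.
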